9.2 Reporting

Subjects will be carefully monitored during the study for possible AEs. Any AE that occurs between the day of the procedure and the end of study participation will be fully evaluated by the investigator.

The Site will report all AEs (anticipated and unanticipated) on an *Adverse Event CRF*. Copies of source documentation which contain significant information related to the event such as progress notes, consultations, nurse's notes, operative reports and subject summaries, etc. may be requested by the

Sponsor or CRO as needed for evaluation of SAEs and ADEs. Copies of such documentation will be obtained from the investigator (or authorized delegate), de-identified as to the subject's identity, and provided to the Sponsor or CRO.

Device malfunctions will be recorded on the LITT Procedure and Discharge CRF. If a device malfunction results in the subject experiencing any untoward medical occurrence, unintended disease or injury, or untoward clinical signs, it will also be reported as an adverse event on an *Adverse Event CRF*.

In case of subject death, it is requested that a copy of the death certificate and a copy of the autopsy report, if applicable, be sent to the Sponsor or CRO when available. Any other source documents related to the death should also be provided to the Sponsor or CRO. In the event that no source documents are available, the PI is required to describe the circumstances of the subject's death in a letter, e-mail or other written communication.

USADEs have special reporting requirements for both the investigator and Sponsor, as described in 21 CFR 812.150:

- Investigator Report: If a subject experiences an USADE, the investigator must notify Monteris and the reviewing IRB as soon as possible, but in no event later than 10 working days after the investigator first learns of the effect.
- Sponsor Report: USADEs will be reported to Food and Drug Administration (FDA), all reviewing IRBs, and participating investigators as soon as possible, but no later than 10 working days, after receiving notice of the USADE(s).

10 STATISTICS

10.1 Endpoint Analysis

Since the objective of this feasibility study is to characterize the performance of LITT, no formal hypotheses tests are planned for any endpoint. Descriptive statistics and exploratory analyses will be used in reporting outcomes for all endpoints.

10.1.1 Primary Endpoint: Analysis of Adverse Events

For adverse events, both event counts and counts of subjects experiencing those events will be reported in tabular summaries. Rates will be reported based on the number of subjects experiencing one or more event as a proportion of all enrolled subjects and these subject rates will serve as the primary analysis.

Adverse event analysis may be repeated for events that occur after the initiation of treatment with rates calculated as a proportion of treated subjects, if it occurs that not all enrolled subjects undergo treatment with LITT.

Event counts, subject counts, and subject rates will also be reported for the following subsets of adverse events: SAE, SADE, UADE, USADE. Adverse events will be further characterized by tabulating the event severity and relationship (see section 9.1).

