6.1 Number of Sites and Subjects

Subjects will be enrolled at up to 8 investigational sites (Sites) in the United States to ensure that data is collected from approximately 30 subjects who undergo laser ablation.

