7.5 Schedule of Visits and Testing Requirements

Table 1 and Table 2 outline the visits, visit windows, and testing requirements at each evaluation time point.

Table 1: Visits and Testing Requirements and Data Collection Summary (Baseline through Month 12)

Visit Window	Baseline			LITT Proc.	DC	Post-Procedure												
	Within 7 days of enrollment	Day of DC	Within 30 days of Baseline ¹			Day 14	Mo. 1	Mo. 2	Mo. 3	Mo. 4	Mo. 5	Mo. 6	Mo. 7	Mo. 8	Mo. 9	Mo. 10	Mo. 11	Mo. 12
	Visit Type	Icon 1	Icon 2	Icon 3	Icon 4	Icon 5	Icon 6	Icon 7	Icon 8	Icon 9	Icon 10	Icon 11	Icon 12	Icon 13	Icon 14	Icon 15	Icon 16	Icon 17
Inclusion and exclusion criteria	✓																	
Informed consent	✓																	
Demographics	✓																	
Medical, surgical & epilepsy history	✓																	
QOLIE-31	✓													✓				✓
Medication review (epilepsy and non-epilepsy)	✓					✓	✓	✓	✓	✓	✓	✓	✓	✓	✓	✓	✓	✓
Physical exam	✓						✓	✓						✓				✓
Neurological exam	✓						✓	✓	✓				✓			✓		✓
Formal visual field testing	✓													✓				
Serum pregnancy test (if female of child-bearing potential)	✓																	
Neuropsychological testing ²	✓ ³												✓		✓			✓
Functional assessment	✓							✓	✓				✓		✓		✓	✓
Seizure classification assessment	I												U		U			U
Seizure diary	T					T/D	C/D	C/D	C	C/D	C	C	C/D	C	C	C/D	C	C/D
Adverse event monitoring						✓	✓	✓	✓	✓	✓	✓	✓	✓	✓	✓	✓	✓
Treatment criteria																		
LITT treatment						✓												
MRI						✓	✓ ⁴							✓				
Surgical pain VAS						✓	✓							✓		✓		✓
Surgical outcome classifications ⁵													✓		✓			✓
Subject satisfaction													✓					✓

Abbreviations: C, collect; D, dispense; DC, discharge; I, initial; LITT, laser interstitial thermal therapy; Mo., month; MRI, magnetic resonance imaging; proc., procedure; QOLIE-31, Quality of Life in Epilepsy - 31; T, training; U, update; VAS, visual analog scale.

¹ Surgery may be performed >30 days after the Baseline Visit if needed to accommodate neuropsychological test scheduling.

² See Appendix C for details of the neuropsychological testing at each visit. These can be performed on a separate day than the Baseline visit.

³ Prior neuropsychological testing may be used for Baseline if the testing was conducted within 6 months prior to the Baseline visit and there were no significant changes to the subject's AEDs or changes to the subject's clinical condition that may affect cognitive function.

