9 ADVERSE EVENTS

9.1 Definitions

Adverse Event

An adverse event (AE) is any untoward medical occurrence, unintended disease or injury, or untoward clinical signs whether or not related to the investigational medical device. This includes events related to the medical device and events related to the procedures involved.

Disease signs and symptoms that existed prior to study participation are not considered AEs unless the condition worsens in intensity or frequency during the study.

Collection of AEs will start on the day of the procedure and will be assessed and reported throughout the study. Investigators must obtain all information available to determine the causality and outcome of the AE and to assess whether it meets the criteria for classification as a serious adverse event (SAE) requiring immediate notification to the Sponsor or CRO. All reported AEs will be documented on the CRF. All AEs will be followed until resolution or PI determination that the subject's condition is stable.

The following are not considered adverse events for this study:

- Any normal expected postoperative complaints or symptoms unless the event involves a clinically significant change in severity or duration of symptoms, or requires clinical intervention that is different from ordinary postoperative care. Expected postoperative complaints and findings include, but are not limited to: headache, edema (on MRI), nausea and vomiting, and postoperative pain.
- Any condition that is recorded as pre-existing on the Baseline CRF, unless there is a worsening of that condition in terms of nature, severity, or degree of incidence.
- Planned hospitalization for a pre-existing condition or a procedure required by the protocol, without serious deterioration in health.

Adverse Device Effect

An adverse device effect (ADE) is an AE related to the use of the study device.

This definition includes AEs resulting from insufficient or inadequate instructions for use, deployment or operation, or any malfunction of the medical device. This definition also includes any event from an error in usage or from intentional misuse of the medical device.

Serious Adverse Event

A serious adverse event (SAE) is an AE that:

- Led to death;
- Led to serious deterioration in the health of the subject, that resulted in:
 - a life-threatening illness or injury, or

- a permanent impairment of a body structure or a body function, or

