11.1 Risks

As with any surgical procedure, the NBS involves some risks. The following potential risks or discomforts may be associated with the surgical procedure or the NBS. In addition, the list includes possible risks associated with the use of the NBS in an epilepsy population.

The frequency and severity of adverse events can vary, and may necessitate additional medical intervention, including surgery.

Agitation	Deep venous thrombosis	Obtundation
Anemia	Depression	Paralysis
Brain aneurysm	Difficulty hearing	Personality or cognitive changes (e.g. mood, memory, attention and thinking ability)
Anxiety	Difficulty speaking	Permanent neurological deficit
Aphasia	Difficulty swallowing	Pneumonia
Ataxia or loss of body coordination	Difficulty walking	Pain at incision site
Atelectasis	Hypotension	Pulmonary or other air embolism
Bacteremia or sepsis	Increased seizures	Reaction to anesthesia or other drugs
Bleeding into or around the brain	frequency/duration or severity, new seizure type, or status epilepticus	Stroke or transient ischemic attack (TIA)
Blurry vision/visual disturbance	Infection, local or generalized	Sudden unexpected death in epilepsy (SUDEP)
Cerebral infarction	Injury to blood vessels	Thromboembolism
Coma	Injury to brain tissue	Tingling or numb sensations in the body
Complete or incomplete hemiparesis	Insomnia	Tissue damage
Death	Intestinal toxicity	Unconsciousness
Decreased energy	Loss of mental function	Wound dehiscence
Drowsiness	Muscle weakness	
Edema	Myocardial infarction	
Failure of central regulation	Nausea/vomiting	
Fever	Nerve paralysis	
Headache		
Hypertension		

Additional possible risks from the evaluations required during this study (but not directly related to the use of the NBS) include:

Laboratory Testing Risks

For the pregnancy test, a blood sample will be taken by inserting a needle into a vein in the arm. Some risks of this procedure include fainting, infection, bruising, formation of a blood clot, pain, and/or bleeding at the site of the needle puncture.

Pregnancy Risks

The effects of LITT during pregnancy are unknown, and it is possible that harmful side effects could occur to both the mother and unborn child. For this reason, pregnant subjects are excluded from participation in this study. If the subject is a woman of childbearing age capable of becoming pregnant, they will be given a pregnancy test prior to entry into the study and again prior to the procedure.

Neuropsychological Testing Risks

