APPENDIX B SEIZURE CLASSIFICATION AND SUBJECT DIARY

Seizure Classification

At the Baseline visit, the investigator or authorized delegate will collect seizure information from the subject and/or caregiver. Information about each seizure type will be collected on a *Seizure Classification - Initial* CRF. Based upon the definition provided by the subject/caregiver, the investigator will classify the seizure based on the International League Against Epilepsy (ILAE) definitions (see Table 4). As subjects may experience multiple kinds of seizures within one class (e.g., two kinds of simple partial seizures), each seizure will be assigned a *seizure letter*. Seizure letters will be assigned alphabetically starting with A.

**Table 4: Seizure Classification
(International League Against Epilepsy)**

Focal Seizures
Without impairment of consciousness or responsiveness
With observable motor or autonomic components
Involving subjective sensory or psychic phenomena only
With impairment of consciousness or responsiveness
Evolving to a bilateral, convulsive seizure
Generalized Seizures
Absence
Typical
Atypical
Myoclonic absence
Eyelid myoclonia
Myoclonic
Myoclonic
Myoclonic atonic
Myoclonic tonic
Tonic
Clonic
Tonic clonic
Atonic
Unclassified Seizures
Epileptic spasms – focal or generalized
Seizure type is unclassified

If at any time during the study the subject experiences a new type of seizure, a new *Seizure Classification - Initial Report* CRF and an *Adverse Event* CRF will be completed. A *Seizure Classification - Update* CRF will be completed if there are any *changes* to previously reported seizure types. At a minimum, the *Seizure Classification - Update* CRF will be completed for each seizure type at the Month 3, Month 6, and Month 12 visits.

Retrospective Seizure Data Collection

Retrospective seizure frequency data will be collected at the Baseline visit. Retrospective reporting will be based on the subject's seizure history and, if available, a subject diary. Although 3 months of seizure frequency data is needed to determine eligibility, seizure count data for the 12 months prior to baseline will be collected, if available.

Diary

The Sponsor will provide a standard diary on which the subject and/or caregiver can record seizure activity. Each diary contains the following information:

- A "key" to the seizure types correlating the assigned seizure letter to the subject's usual descriptor of the seizure (e.g., Seizure Type A = the "big one")

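### The primary AE rate divides by all enrolled subjects although AEs are collected only from the procedure day, so any loss before surgery dilutes the headline safety rate

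*Protocol*

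**What the plan says.** **Collection window.** Protocol 9.1 states "Collection of AEs will start on the day of the procedure". Section 9.2 repeats the window for investigator evaluation: "Any AE that occurs between the day of the procedure and the end of study participation".

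**Denominator.** Protocol 10.1.1 states "Rates will be reported based on the number of subjects experiencing one or more event as a proportion of all enrolled subjects" and makes these subject rates the primary analysis. SAP 11.1.1 also divides by enrolled subjects and calls the result primary.

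**Treated-subject rate.** Both documents say only that the AE analysis *may* be repeated on treated subjects. The protocol adds a condition: "if it occurs that not all enrolled subjects undergo treatment with LITT".

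**Populations.** Protocol 10.2.2 and SAP 10 say the Treated Set (thermal energy delivered) is the better basis for judging performance, and they make Enrolled Set analyses the optional repeat. For AEs, 10.1.1 and 11.1.1 reverse that order.

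**Enrollment.** Protocol 7.4 counts a patient as enrolled once all criteria are met and consent is signed, which is before surgery. The recruitment target is set on ablation and not on enrollment: "to ensure that data is collected from approximately 30 subjects who undergo laser ablation" (6.1).

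**The concern.** A rate over all enrolled subjects makes sense when AEs are collected from enrollment. The SAP names revision A as its protocol (section 3) and fits that picture: its Table 1 has AE monitoring at pre-procedure visits, and 11.1.1 has an AE phase before the procedure. Revision B's collection window leaves that phase essentially empty, yet the enrolled denominator remains.

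A subject who enrolls and is never operated on then lowers the rate without having been observed for AEs in the same way. Safety is the primary endpoint, and protocol 10.2.4 says the results should help plan a larger pivotal trial. A reader who takes the primary AE rate as the risk of the procedure would take a figure that is too low.

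**Working it through.** **1. The plan's own figure.** Protocol 10.2.4 and SAP 9 give about an 80% chance of seeing, in 30 subjects, an AE with 5% per-subject probability. 1 − 0.95^30 = 0.785, so the figure reproduces.

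**2. The dilution.** Let X be subjects with at least one AE, O those operated on (LITT attempted) and E those enrolled. If X comes only from O, then

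X/E = (X/O) × (O/E), and the relative understatement is 1 − O/E.

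This is very close but not exact, for two reasons. Protocol Appendix B requires an AE form for a new seizure type, which opens a narrow route before surgery: "If at any time during the study the subject experiences a new type of seizure". Collection also starts on the procedure *day*, so an event that day is recorded even if the procedure is then cancelled.

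**3. Size.** O = 30 is the target in protocol 6.1. The values of E are assumptions, because revision B states none.

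| E (assumed) | O/E | Relative understatement | A 5% event has expected primary rate |
|---|---|---|---|
| 30 | 1.000 | 0% | 5.0% |
| 31 | 0.968 | 3.2% | 4.8% |
| 33 | 0.909 | 9.1% | 4.5% |
| 36 | 0.833 | 16.7% | 4.2% |

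With 6 affected subjects (assumed) and Clopper-Pearson 95% limits:
- 6/30 = 20.0% (7.7 to 38.6)
- 6/33 = 18.2% (7.0 to 35.5)
- 6/36 = 16.7% (6.4 to 32.8)

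With no affected subject, the upper limit is 1 − 0.025^(1/E): 11.6% for 0/30, 10.6% for 0/33 and 9.7% for 0/36. Subjects who were never operated on appear to add safety information.

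**4. Why the Treated Set alone is not the remedy.** It leaves out attempts stopped before thermal delivery. Assume 32 attempts, 2 of them stopped, and 6 of the 30 treated subjects with an AE. The treated rate is 6/30 = 20.0%. The attempted rate is 6/32 = 18.8%, 7/32 = 21.9% or 8/32 = 25.0% if 0, 1 or 2 of the stopped attempts have an AE.

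The attempted denominator has a limit of its own, because stopped attempts are followed for only 1 month (protocol 7.6.2). If 18 of 30 treated subjects have an AE by 24 months and the 2 stopped attempts have none, 18/32 = 56.3% against 18/30 = 60.0%. That is a relative shortfall of 1 − 30/32 = 6.25%. Both rates are therefore needed.

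**The case against.** The best case for the plan is that little may be lost. Protocol 7.4 enrolls only patients who meet all criteria, so those found ineligible after consent are not enrolled on that wording, and O/E may be close to 1. Subject counts are mandatory (10.1.1), and SAP 12.2 reports how many enroll, leave before LITT and undergo LITT. The plan foresees untreated enrollees and supplies a treated-subject analysis. No hypothesis test or performance goal uses the rate, and the shifts above sit well inside the confidence intervals. The enrolled rate also already counts events in failed attempts, which the treated rate does not.

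Most of this stands as a limit on size and consequence. It does not remove the mismatch: the analysis named primary is still the diluted one, and the matching one is still optional.

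A reader might infer more than the documents support:

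- *That the rate is understated by one third.* SAP 9 allows up to 45 enrolled for about 30 procedures, but that SAP was written for revision A, with visits from Week -12 before the procedure. It is no estimate for revision B.
- *That revision B predicts attrition.* It only allows time and reasons for it. Table 1, footnote 1 says "Surgery may be performed >30 days after the Baseline Visit if needed", and 7.8 lists withdrawal at the subject's request. Section 11.1 says of women able to become pregnant that "they will be given a pregnancy test prior to entry into the study and again prior to the procedure", but revision B's Table 1 shows only the Baseline test, so that sentence is weak evidence.
- *That the 80% detection chance is wrong.* Subjects who are not operated on add no chance of an event, so 78.5% holds for any E.

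**Conclusion.** The point holds. Revision B's AE window and the enrolled denominator do not match. Apart from the narrow routes named above, a subject lost before surgery can only lower the primary AE rate. The understatement is 1 − operated/enrolled: zero if everyone enrolled is operated on, and 3.2%, 9.1% or 16.7% at assumed enrollments of 31, 33 or 36 with 30 operated. The true size under revision B cannot be read from the documents.

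The denominator itself is not settled. Protocol 7.4 requires all criteria to be met, whereas SAP 12.2 equates signing consent with enrolling and counts those meeting all criteria separately. On the SAP's reading, patients who fail criteria after consent would dilute the rate further.

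It should be fixed because it concerns the primary endpoint and errs in one direction. The documents do not support saying that it would lead to a wrong decision, since nothing is tested against this rate and a reader can largely rebuild the operated-subject rate.

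**What to change.** In protocol 10.1.1 and SAP 11.1.1:

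- Make the primary AE denominator all subjects who reach the procedure day and have LITT attempted, including attempts stopped before thermal delivery. Count AEs from the procedure day, to match 9.1 and 9.2. Leave the time frame of the primary analysis as it is.
- Change the Treated Set AE rate from *may* to *will*.
- Keep the enrolled-subject rate as supportive.
- Print the numbers enrolled, attempted and treated beside each rate.
- List events after failed attempts separately, because those subjects are followed for only 1 month.

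The cost is wording in both documents, settled before any analysis. The headline rate may become slightly less favourable.

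Two related matters need separate attention. Protocol 7.6.2 follows failed attempts for AEs, while 7.8 says related AEs. These passages must be reconciled, and the completeness of AEs in those few subjects depends on the outcome. The SAP's AE phases and enrollment definition should also be brought into line with revision B.

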10.1.2 Primary Endpoint: Analysis of Neuropsychological Testing

For each neuropsychological test, descriptive statistics will be reported for the measured score at baseline and each follow-up visit. In addition, change from baseline will be calculated at each follow-up visit and descriptive statistics will be reported. For each subject, the change from baseline will be categorized as improved, unchanged, or deteriorated based on whether the change exceeds a pre-specified threshold determined by Reliable Change Index (RCI) methodology for that specific neuropsychological test with a 95% confidence level. The threshold thus represents a degree of change that is unlikely (<2.5% chance in either direction) to occur due to measurement error of the neuropsychological instrument alone. The proportion of patients in each category at each follow-up time will be tabulated.

As there is no control group for comparison, any observed changes in neuropsychological function will need to be evaluated in comparison to longitudinal changes observed in prior longitudinal studies of similar subjects, examining typical changes in both subjects that have and have not undergone invasive therapy.

10.1.3 Secondary Endpoint: Analysis of Seizure Outcomes

Seizure frequency will be characterized by calculating the rate of seizure occurrence within specific follow-up time periods (count of reported events/reported time frame). Follow-up time periods of interest include all follow-up and between-visit follow-up periods (e.g., procedure to Month 3) to characterize the longitudinal course of seizure frequency. For each time period, descriptive statistics of subject-specific rates characterize the distribution of observed seizure rates. The change from baseline in seizure rates may also be calculated by calculating the difference in rates between a follow-up period and the baseline rate of seizures occurring prior to treatment (count of reported events/reported time frame). Since subjects may have different baseline seizure rates, the relative reduction (follow-up rate/baseline rate - 1) will also be calculated to scale the degree of improvement relative to the baseline rate. These analyses may be repeated for subsets of seizures with specific classifications to characterize the frequency of different seizure types.

The main analysis of seizure frequency will include subjects with at least 70 completed diary days in each 3-month period from procedure through 12 months and at least 140 diary days in each 6-month period from 12 months through study completion. To account for incomplete diary completion, sensitivity analyses may be performed by including subjects with less than the required level of diary completion and by using the number of days with completed diary entries to determine the denominator in the event rate calculation.

Seizure frequency may be further characterized by calculating the proportion of responders. A responder is a subject whose seizure frequency in a specified 3-month interval is reduced by $\geq 50\%$ as compared to baseline.

Seizure free days may be further characterized by calculating the number of seizure-free days that subjects experience during a specified 3-month interval. In order to make the 3-month

follow-up intervals comparable, the number of days actually recorded will be prorated to an 84-day intervals.

Surgical outcome classification will be reported by tabulating the Engel and ILAE class frequency distribution at each scheduled follow-up among subjects completing that follow-up visit. The change in surgical classification between visits may be described by performing a cross-tabulation of the classifications at subsequent visits.

Freedom from seizures with altered awareness will be reported using Kaplan-Meier curve analysis of the time to first seizure, as reported in patient diaries. The time to event analysis will exclude seizures that occur within the first 4 weeks post-procedure. The Kaplan-Meier analysis may be repeated for freedom from all seizures, seizures with other classifications, and inclusion of seizures within the first 4 weeks post-procedure. The log-log transformation will be used to calculate 95% confidence intervals. The time point of primary interest is 24 months.

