6.3.1 Study Inclusion Criteria

Subjects must meet all of the following inclusion criteria:

1. Diagnosis of unilateral medial temporal lobe epilepsy (MTLE) confirmed clinically and with either (1) ictal scalp recording and MRI evidence of mesial temporal sclerosis or (2) intracranial ictal onset consistent with hippocampal origin
2. Subject's seizures are distinct, stereotypical events that can be reliably counted.
3. Based on medical record, history of an average of at least 1 complex partial or secondarily generalized seizure compatible with MTLE per month for a minimum of the last 12 months prior to the Baseline visit (i.e., at least 12 qualifying seizures in the 12 months prior to the Baseline visit). *(Seizures occurring during inpatient assessment in an epilepsy monitoring unit should not be included in the average).*
4. Subject is on stable antiepileptic drugs (AEDs) for 30 days prior to the Baseline visit and compliant with medication use (as reported by the subject). Stable is defined as no new or discontinued AEDs and no changes to AED total daily dose. *(Exception: (1) temporary changes or discontinuation of AEDs for the purposes of diagnostic or medical procedures during the 30 days preceding the Baseline visit and (2) acute, intermittent use of benzodiazepines or other rescue medications.)*
5. Subject has met the criteria for a medial temporal lobe resection based on the Site's standardized pre-surgical evaluation.
6. Subject is deemed a LITT candidate by the center's epilepsy evaluation team.
7. Subject is 18 years or older at the time of consent.
8. Subject can be reasonably expected to maintain a seizure diary alone or with the assistance of a caregiver.
9. If female, must be postmenopausal, surgically sterile, or, if of childbearing potential, have a serum pregnancy test with a negative result at the Baseline visit and practicing effective contraception.³
10. Subject or legally authorized representative is able to provide appropriate consent to participate.
11. Subject is able to complete regular office and telephone appointments per the protocol requirements.
12. Subject speaks English or Spanish as a primary language. If Spanish, the Site must be able to provide a translated (IRB-approved) consent form and the Site's neuropsychologist must be willing and able to assess the subject in Spanish.

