Class 4: Four seizure days per year to 50% reduction of baseline seizure days³; ± auras

Class 5: Less than 50% reduction of baseline seizures days to 100% increase of baseline seizure days; ± auras

Class 6: More than 100% increase in baseline seizure days; ± auras

¹ Auras are only counted if they are short in duration and similar or identical to the preoperative auras.

² A "seizure day" (for the purposes of this classification) is defined as a 24-hour period with one or more seizures. This may include an episode of status epilepticus.

³ The number of "baseline seizure days" is calculated by determining the seizure-day frequency during the 12 months before surgery, with corrections for the effects of AED reduction during diagnostic evaluations prior to the index procedure.

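### The baseline seizure rate lacks the monitoring-unit exclusion and diagnostic-taper correction used elsewhere in the plan, so relative reduction can favour LITT for subjects whose work-up falls inside the baseline window

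*Protocol*

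**What the plan says.** The documents use three pre-treatment seizure measures and treat work-up seizures differently in each.

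- **Eligibility** (Protocol 6.3.1, criterion 3): "Seizures occurring during inpatient assessment in an epilepsy monitoring unit should not be included in the average".
- **ILAE class** (Protocol Appendix D, Table 8 footnote 3; repeated in SAP Appendix B): baseline seizure days come from the 12 months before surgery, "with corrections for the effects of AED reduction during diagnostic evaluations prior to the index procedure".
- **Seizure-rate change** (Protocol 10.1.3; same wording in SAP 11.1.3): "the baseline rate of seizures occurring prior to treatment (count of reported events/reported time frame"), with no exclusion or correction. SAP 12.4 divides events by days of data collection and drops only days without data.

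The third measure feeds an output the protocol commits to: "the relative reduction (follow-up rate/baseline rate - 1) will also be calculated". It also feeds the optional responder proportion: "A responder is a subject whose seizure frequency in a specified 3-month interval is reduced by" at least 50% against baseline.

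In Protocol Rev B the diary starts the day after discharge, so the baseline is retrospective. Appendix B says "Retrospective reporting will be based on the subject's seizure history and, if available, a subject diary" and that "seizure count data for the 12 months prior to baseline will be collected, if available". It states no EMU exclusion. Section 10.1.3 does not say which baseline window the rate uses. The SAP cites Protocol Rev A and compares responders with a 3-month Baseline Phase that Rev B no longer contains.

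**The concern.** Inclusion criterion 1 requires an ictal scalp recording or an intracranial ictal onset, so subjects will have had seizures recorded during work-up. Criterion 4 tolerates "temporary changes or discontinuation of AEDs for the purposes of diagnostic or medical procedures during the 30 days preceding the Baseline visit". A stay or taper can therefore fall inside a retrospective baseline window. The follow-up schedule contains no corresponding stay.

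If the formula is applied as written, seizures provoked by the work-up enter only the pre-treatment side of the comparison. Part of the later fall would then occur whether or not LITT did anything, and with no control group nothing in the study would reveal it. Protocol 10.2.4 says the results are meant to inform planning of a larger pivotal trial, so an inflated percent reduction would carry forward. It could not be corrected later unless EMU and taper dates had been recorded.

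The baseline rate also defines the baseline-frequency tertiles (SAP 13) and is a covariate in the site Poisson model (SAP 19). The SAP's Engel term for worthwhile improvement, a reduction of at least 50% from baseline, is likewise uncorrected. The medication sensitivity analysis in SAP 18.1 censors visits after a drug change and does not adjust the baseline count.

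**Working it through.** The plan gives no figure for this quantity. Its one design figure is the chance of seeing at least one event of 5% probability in 30 subjects. This reproduces (1 - 0.95^30 = 0.785, stated as about 80%) but has no bearing here.

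**Inputs**
- r, habitual monthly rate: 1 (Rev B entry floor, 12 seizures in 12 months) or 3 (floor listed in SAP 10).
- T, baseline window in months: 12 (the retrospective count in Rev B) or 3 (the SAP's Baseline Phase).
- e, EMU or taper seizures counted in the window: an assumption, because the documents give none. Range used: 2 to 6.
- f, true follow-up rate divided by habitual rate (1 = no effect).

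**Formula.** With b = r x T habitual seizures in the window, the recorded baseline rate is (b + e)/T. The apparent change is f x b/(b + e) - 1.

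**Step 1: no true change (f = 1), window and floor from the same design**

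| Setting | b | e | Apparent change |
|---|---|---|---|
| Rev B: 1 per month, 12 months | 12 | 2 | 12/14 - 1 = -14.3% |
| same | 12 | 4 | 12/16 - 1 = -25.0% |
| same | 12 | 6 | 12/18 - 1 = -33.3% |
| SAP: 3 per month, 3 months | 9 | 4 | 9/13 - 1 = -30.8% |

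A higher rate on the longer window dilutes the effect: at 3 per month over 12 months, e = 4 gives 36/40 - 1 = -10.0%.

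**Step 2: the 50% responder line.** It is reached when f x b/(b + e) <= 0.5, that is, e >= b(2f - 1).
- f = 1: e must be at least 12 (Rev B pairing) or 9 (SAP pairing).
- f = 0.6, a true 40% reduction: e must be at least 0.2b, which is 2.4 or 1.8, so 3 or 2 seizures. Check: 1 - 0.6 x 12/15 = 52.0%; 1 - 0.6 x 9/11 = 50.9%.

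**Step 3: chance variation.** Counts were simulated as Poisson with no treatment effect, a 3-month follow-up interval and at least one habitual baseline seizure. The chance of responder status is:

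| Setting | e = 0 | e = 3 | e = 5 |
|---|---|---|---|
| 1 per month, 12-month baseline | 22% | 30% | 36% |
| 3 per month, 3-month baseline | 10% | 21% | 31% |

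**Step 4: the undefined window.** At 1 per month on a 3-month window (b = 3), e = 2, 4 or 6 gives 3/5 - 1 = -40.0%, 3/7 - 1 = -57.1% or 3/9 - 1 = -66.7%. No analysis text pairs that floor with that window, but Rev B does not exclude it.

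**Step 5: after the fix.** With work-up seizures and days removed, e = 0 and the apparent change is f - 1: 0% for no effect and -40% for a true 40% reduction.

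**The case against.** The strongest reply is that silence is not inclusion. Rev B has a single retrospective seizure collection, linked to eligibility, and criterion 3 already tells sites to leave EMU seizures out of the eligibility average. A site may apply the same rule to the whole history. This stands to the extent that no text instructs sites to count these seizures. It does not remove the problem: the written formula carries no exclusion, and unstated practice across up to 8 sites would leave baselines that are not comparable.

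Timing is a second reply, and it also stands. Criterion 1 sets no date for the ictal recording, and criterion 4 permits drug changes without showing how often they fall in the window. Under the SAP's prospective phase, which starts within 7 days of enrollment, the qualifying recording should normally come first. A subject monitored before the window contributes no bias.

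Third, other features can work against LITT. Drugs are held stable only through Month 12, with exceptions. The 4-week post-procedure exclusion is stated for Kaplan-Meier and for Engel and ILAE class, but not for seizure rates, so early postoperative seizures can raise the follow-up rate. The net direction across the cohort is therefore not established, although the direction of this one component is clear.

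A reader might infer that the reported LITT benefit is overstated, or that a subject with no benefit would ordinarily be counted as a responder. The documents do not support either. The first needs facts on timing and counts that they do not contain. The second pairs Rev B's 1-per-month floor with a 3-month window that Rev B states only for eligibility, and that the SAP uses with a floor of 3 per month.

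**Conclusion.** The inconsistency is real and the plan should be changed. The bias is conditional: it needs an EMU stay or diagnostic taper inside the baseline window, with its seizures reported. For such a subject the apparent change with no true effect is -14% to -33% (2 to 6 EMU seizures, Rev B floor, 12-month baseline) or -31% (4 EMU seizures, SAP floor and 3-month baseline). Neither setting alone makes an unchanged subject a responder on expected rates, but a few EMU seizures can carry a true 40% reduction past the 50% line. Larger distortions arise only if a 3-month window is used at about 1 per month, which remains possible because Rev B leaves the window open.

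The EMU counts are assumptions, and the cohort-level effect cannot be calculated from the documents. The analyses concerned are secondary and descriptive, and only the relative reduction is a firm commitment. Safety, Kaplan-Meier seizure freedom and QOLIE-31 do not use this rate, and ILAE class already carries its own correction.

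**What to change.** In Protocol 10.1.3 and SAP 11.1.3:

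1. State one baseline window for the seizure rate, consistent with Rev B, and replace the SAP's references to the 3-month Baseline Phase.
2. Define the baseline rate as seizures divided by days, leaving out both the seizures and the days of EMU stays and of drug reduction for diagnostic evaluation. Write the rule out in full, because criterion 3 (an exclusion) and the ILAE footnote (an unspecified correction) are not the same rule.
3. Record the dates of those stays and reductions with the epilepsy history, and the seizures that occurred in them.
4. Use this rate for change, relative reduction, responder status and the baseline-frequency tertiles.
5. Add a sensitivity analysis that includes the excluded seizures and days.

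The cost is a short text change in each document and a little extra data collection. Reported reductions may be slightly less favourable.
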